2.8.3.2 Vital signs

Vital sign assessments will be performed in order to characterize basic body function. The parameters collected are weight (kg), body temperature (°C), pulse rate (beats per minute), systolic and diastolic blood pressure (mmHg).

Vital signs shift table based on values classified as notable low, normal, notable high or notable (high and low) at baseline and worst post-baseline will be produced for pulse rate.

Patients with clinically notable vital sign abnormalities will be listed. All vital sign assessments will be listed by patient and vital sign parameter. In the listings, clinically notable values will also be flagged.

The criteria for clinically notable values are defined in [Table 2-2](#).

Table 2-2 Clinically notable vital sign ranges.

Body temperature (°C)	High	≥39.1°C	
	Low	≤35.0°C	
Weight	High	Increase from baseline ≥ 10%	
	Low	Decrease from baseline ≥ 10%	
Pulse rate (beats per minute)	High ²	12-18 months	> 140
		18-24 months	> 135
		2-3 years	> 128
		3-4 years	> 123
		4-6 years	> 117
		6-8 years	> 111
		8-12 years	> 103
	Low ²	12-15 years	> 96
		15-18 years	> 92
		12-18 months	< 103
		18-24 months	< 98
		2-3 years	< 92
		3-4 years	< 86
		4-6 years	< 81
6-8 years	< 74		

8-12 years	< 67
12-15 years	< 62
15-18 years	< 58

¹[Systolic](#) and diastolic blood pressure will be listed individually.

²Fleming S, Thompson M, Stevens R, et al. Normal ranges of heart rate and respiratory rate in children from birth to 18 years of age: a systematic review of observational studies. Lancet 2011; published online March 15. DOI: 10.1016/S0140-6736(10)62226-X.

2.9 Performance status

Performance status will be assessed using the Karnofsky or Lansky performance scales, depending on the patient’s age. The score, reported on an ordinal scale of 0-100 provides a rough measure of the patients’ well-being, including ability to conduct activities of daily living and functional capacity. Patients are classified as to their functional impairment status using the Karnofsky performance assessment (patients greater than 12years of age) or the Lansky performance status (patients 12 years of age and younger). The definition of scores in relation to performance based on the Karnofsky performance assessment is given in [Table 2-3](#). The definition of scores based on the Lansky performance assessment is given in [Table 2-4](#).

Table 2-3 Karnofsky performance status scale (for patients greater than 12yrs of age)

General category	Grade	Karnofsky score interpretation
Able to carry on normal activity and to work; no special care needed	100%	Normal no complaints.
	90%	Able to carry on normal activity; minor signs or symptoms of disease.
	80%	Normal activity with effort; some signs or symptoms of disease.
Unable to work; able to live at home and care for most personal needs; varying amount of assistance needed.	70%	Cares for self; unable to carry on normal activity or to do active work.
	60%	Requires occasional assistance, but is able to care for most of his personal needs.
	50%	Requires considerable assistance and frequent medical care.
Unable to care for self; requires equivalent of institutional or hospital care; disease may be progressing rapidly.	40%	Disabled; requires special care and assistance
	30%	Severely disabled; hospitalization is indicated though death not imminent.
	20%	Very sick; hospitalization necessary; active supportive treatment necessary.
	10%	Moribund; fatal processes progressing rapidly.
	0%	Dead

Table 2-4 Lansky score (for patients 12years of age and younger)

General category.	Score	Lansky status
Able to carry on normal activity and to work; no special care needed	100	Fully active, normal
	90	Minor restrictions in physically strenuous activity
	80	Active, but tires more quickly
	70	Both greater restriction of play and less time spent in play activity

General category.	Score	Lansky status
Mild to moderate restriction	60	Up and around, but minimal active play; keeps busy with quieter activities
	50	Gets dressed but lies around much of the day; no active play but able to participate in all quiet play and activities
Moderate to severe restriction/dead	40	Mainly in bed; participates in quiet activities
	30	Bed-bound; needs assistance even for quiet play
	20	Often Sleeping; play entirely limited to very passive activities
	10	No play; does not get out of bed
	0	Unresponsive

Performance status will be summarized separately for the Karnofsky and the Lansky score based on FAS. Shift tables of scores at baseline to worst post-baseline status by general category will be summarized. Performance status at each time point will be listed.

2.10 Pharmacokinetic endpoints

Blood samples for PK analysis of ceritinib are collected during the dose escalation part and expansion part of the study as per protocol. All PK analyses will be performed based on the PAS unless otherwise specified.

During the dose escalation phase of the study, blood samples for full plasma concentration-time profile of ceritinib are collected over 24 hours on Cycle 1 Day 1 and on Cycle 2 Day 1 at the following scheduled time points: pre-dose, 2, 4, 6 and 24 hours post-dose. Trough PK samples are also collected pre-dose on Day 1 of Cycle 3-4 and Day 15 of Cycle 1.

During the expansion phase, blood samples for full plasma concentration-time profile of ceritinib are collected over 24 hours on Cycle 2 Day 1 at the following scheduled time points: pre-dose, 2, 4, 6 and 24 hours post-dose. Trough PK samples will be collected on Day 1 of Cycle 1-4 at the MTD and/or RDE.

Only PK plasma concentrations with non-missing sampling data and time, and for which the last dose date and time prior to the PK sample draw are non-missing will be included in the PK analysis. Unscheduled samples are not included in any analysis, but these samples will be listed using PAS and flagged in the corresponding concentration listing.

PK parameters

Pharmacokinetic parameters will be determined using non-compartmental method(s), using Phoenix WinNonlin (Pharsight, Mountain View, CA.), The PK parameters listed in [Table 2-6](#) will be estimated and reported, as appropriate.

Among the parameters, the following are considered primary: AUC_{tau}, C_{min}, C_{max}, T_{max}; and the following are considered secondary: CL_{ss}/F, R_{acc}. Those not designated as primary or secondary will be listed only.

Table 2-5 Noncompartmental pharmacokinetic parameters

AUC _{tau}	The AUC calculated to the end of the dosing interval, tau.
--------------------	--

Cmin	Observed concentration at the end of a dosing interval (taken directly before next administration).
Cmax	The maximum observed plasma, blood, serum, or other body fluid drug concentration
Tmax	The time to reach maximum (peak) plasma, blood, serum, or other body fluid drug concentration
T1/2,acc	Effective half-life can be calculated from Racc.
CLss/F	Apparent oral total body clearance of drug from the plasma calculated from steady-state exposure
Racc	Accumulation ratio calculated using AUCtau values obtained from a dosing interval at steady-state divided by AUCtau at day 1

Data handling principles

Concentration values below the lower limit of quantitation (LLOQ) (< 1.0 ng/mL) will be displayed in listings as zero with a flag and handled as zero in the calculations of summary statistics except for geometric means and associated CVs where they will be set to missing. Any missing PK parameters will not be imputed.

LDK378 concentrations

Summary statistics, including n, mean, SD, coefficient of variation CV (%) for mean, geometric mean, geometric CV (%), median, minimum and maximum, will be presented for evaluable PK plasma concentration of LDK378 following the general reporting rule for PK, by treatment and scheduled time point for both full PK profile and trough PK concentrations, separately for fasted and fed patients and for escalation phase and expansion phase. For patients with full PK profile on Cycle 1 Day 1 or Cycle 2 Day 1, corresponding graphical presentations of the plasma concentration profiles will be provided by treatment using arithmetic mean (+/- SD) and geometric mean values at each scheduled time point. The individual plot will also be provided.

LDK378 PK parameters

Primary and secondary PK parameters will be summarized using the same reporting approach as for LDK378 concentrations, by treatment, separately for Cycle 1 Day 1 and Cycle 2 Day 1 for fasted and fed patients in the escalation and expansion phase. For Tmax, only median, minimum and maximum will be presented.

All PK parameters and concentration data will be listed by treatment using PAS.

Dose proportionality (DP) analysis

DP analysis at single dose (Cycle 1 Day 1) and steady state (Cycle 2 Day 1): Data from both dose-escalation phase and expansion phase will be used. AUC0-24h and Cmax will be analyzed. All dose levels will be included.

DP will be assessed via the following model as well as graphical presentations.

DP is analyzed by fitting a linear model as described below.

$$\ln(\text{PK}) = \alpha + \beta * \ln(\text{actual dose}),$$

where PK is the PK parameter, AUC₀₋₂₄ or C_{max}, and actual dose (mg/m²) is defined as dose divided by BSA.

The estimate and its 90% confidence interval (CIs) for β in each case are reported. As an informal comparison, the estimates and CIs for β are compared to the target dose-proportionality range, calculated by the following formula (Smith, 2000).

Lower bound of target dose-proportionality range of β : $1 + \ln(0.8)/\ln(\text{dose range})$

Upper bound of target dose-proportionality range of β : $1 + \ln(1.25)/\ln(\text{dose range})$

Dose range is the highest actual dose/lowest actual dose, for which data are used for the dose proportionality analysis. The dose range may or may not be the same for all parameters.

This analysis is not prospectively powered for the result to fall into the target range, and therefore the actual result rather than the comparison itself should be emphasized when interpreting data.

Trough concentration (C_{trough})

Trough PK samples will be collected at the following time points:

- 0 hour pre-dose samples on C1D1, C1D8, C1D15, C2D1-C6D1 in all patients
- 0 hour pre-dose sample on C1D2 (i.e. 24 hour post-dose samples on C1D1), and C2D2 (i.e.

24 hour post-dose samples on C2D1) for patients with full PK collection

The trough concentrations obtained throughout the study will be plotted over time by treatment arm using PAS. Only time points with $n \geq 4$ trough observations will be shown on the figure.

No model-based analyses will be conducted.

Average C_{trough}

Average trough concentration will be used in the exposure response analyses. Each patient may have one or more C_{trough} values. The average C_{trough} considering the distribution of PK is generally lognormal is defined as:

$C_{trough_{avg}} = \text{geometric mean (all } C_{trough} \text{ for each patient)}$, considering the distribution of PK concentration is generally lognormal.

Ceritinib trough concentration included in calculating the average **must fulfill** the following rules:

- For the pre-dose or 24 hour post-dose sample, draw must occur between 18 to 30 hours

after the last dose intake (except for Cycle 1 Day 1), AND

- For the pre-dose or 24 hour post-dose sample, the draw must occur before the next dose

intake, AND

- Additionally, a sample can be considered non-evaluable as per scientific judgment of the

clinical pharmacology expert even if the above criteria are fulfilled. Reason will be documented.

The criteria have been modified over evaluable trough concentration as defined in PAS by removing the following three rules:

- No vomiting occurs within 4 hours following the last dose intake prior to the PK sample draw,
- The patient takes study drug according to the originally assigned dose for at least 5 consecutive days without interruption or dose modification prior to the PK sampling day (except for Cycle 1 Day 1),
- The patient takes study drug under the originally assigned prandial conditions, i.e., dose

administered without food for patients randomized to the treatment arm of 750 mg fasted, or dose administered with food for patients randomized to the treatment arm of 450 mg with low-fat meal or 600 mg with low-fat meal, for at least 5 consecutive days prior to the PK sampling day (except for Cycle 1 Day 1)

This allows exposure-response analyses to take into account the exposure after study drug interruption, dose reduction, vomiting or fail to adhere to the assigned prandial condition for individual patient.

Quartile ranges of C_{trough_avg} are defined as:

- <Q1: <25th percentile
- Q1-<Q2: ≥25th percentile and <50th percentile
- Q2-<Q3: ≥50th percentile and <75th percentile
- ≥Q3: ≥75th percentile

C_{trough_avg} and its quartile values will be used in display of AE.

Inter and intra patient variation

The intra-patient and inter-patient variations will be evaluated using data from patients at MTD with one or more than one evaluable steady state trough PK measurements. Evaluable trough concentration is defined in PAS. For steady state trough concentration, we will only consider trough values collected on or after C1D15 (C1D1 sample will not be used in the analysis). The intra-patient and inter-patient variations will be estimated using random effects model with treatment as a fixed effect and patient as a random effect. See [Section 5.7](#) for more details.

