### **IRB/IEC/REB Approval**

A copy of this amended protocol will be sent to the Institutional Review Board (IRBs)/Independent Ethics Committee (IECs) and Health Authorities.

The changes described in this amended protocol require IRB/IEC approval prior to implementation.

The changes herein affect the Informed Consent. Sites are required to update and submit for approval a revised Informed Consent that takes into account the changes described in this protocol amendment.

## Amendment 6

The dose escalation phase of this study has been completed and 40 patients have been enrolled and treated (25 fasted and 15 fed). Similar recommended LDK378 doses (RDE) were established for both fasted state (510 mg/m^2 once daily, declared on 4 Dec 2014), and fed state (500 mg/m^2 once daily, declared on 12 April 2016). As fed state is more convenient for pediatric patients, it has been decided to complete the recruitment of the expansion phase using this preferred regimen only. The expansion phase, to confirm the dose, is currently recruiting and as of 22 September 16, 20 patients have been enrolled (7 fasted and 13 fed). Overall, 19 patients are currently ongoing in total (6 recruited in escalation phase and 13 in the expansion phase).

The primary purpose of this amendment is to revise the dose reduction steps for LDK378. Considering the recommended doses established for fed and fasted state are similar, the dose reduction schedule has been revised to be applicable for both states.

In addition, the schedule of assessments has been revised to reduce frequency of on-site visits after cycle 16: on-site visits on day 1 of odd numbered cycles are replaced by phone calls and local laboratory tests for safety assessments.

Moreover, the pre-dose PK sample and the post-dose ECGs collection at Cycle 1 Day 1 have been removed in the expansion phase as they were no longer required at this time point as no correlation is planned in the expansion.

At last, editorial changes and text corrections were made for clarification, where required.

Changes to specific sections of the protocol are shown in the track changes version of the protocol using red strike through font for deletions and red underlined font for insertions.

The following sections were updated:

- Section 6.3.1: Table 6-3 dose reduction steps for LDK378 was revised based on the recommended dose for expansion

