### 1.2.1.2.4 Clinical pharmacokinetics

In adult patients with tumors characterized by genetic abnormalities in ALK [REDACTED] and in healthy volunteers [REDACTED] and [REDACTED] the single-dose pharmacokinetics of LDK378 in humans has the following features: (1) LDK378 was slowly absorbed, with median peak plasma concentration occurring at approximately 4 to 6 h in patients, and approximately 6 to 8 h in healthy subjects. Following Cmax, LDK378 concentrations declined in a mono-exponential manner. The geometric mean apparent terminal half-life ranged from 31 to 41 h across the 400 to 750 mg dose groups in patients and 36 to 48 h across the 450 to 750 mg dose groups in healthy subjects. (2) Cmax and AUClast increased dose-proportionally following single oral administration of LDK378 across the 50 to 750 mg dose groups. (3) Moderate to high variability in LDK378 PK parameters has been observed in both healthy subjects and patients. Following single oral doses of 450 to 750 mg in healthy subjects when LDK378 was given alone, the inter-subject variability (geometric mean coefficient of variation; CV% range) was 42-74% and 35-72% for AUClast and Cmax, respectively. The corresponding values in patients were 93% and 87% following single oral doses of 50 to 750 mg based on a model developed for dose proportionality analysis.

[REDACTED]

The multiple-dose PK of LDK378 following repeated daily oral dosing in patients has the following features: (1) AUCtau at the maximum tolerated dose and recommended dose of 750 mg increased from first dose with geometric mean accumulation ratios of 4.7 on Cycle 1 Day 8 after 1 week of daily dosing and 6.2 on Cycle 2 Day 1 after 3 weeks of daily dosing, respectively. Evaluation of trough concentration at 750 mg that steady-state was achieved by Cycle 1 Day 15 following 2 weeks of daily dosing. (2) LDK378 demonstrated nonlinear PK over time, as indicated by the observed difference in apparent clearance (CL/F) between single-dose (88.5 L/h at 750 mg) and steady-state at Cycle 2 Day 1 (33.2 L/h at 750 mg). As LDK378 is a substrate as well as a time-dependent inhibitor of CYP3A, it is likely that this PK nonlinearity could be attributed to auto inhibition of LDK378. In contrast with single dose data, Ctrough on Cycle 2 Day 1 after repeated daily dosing increased with dose in a greater than dose-proportional manner.

[REDACTED]

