CYP3A was identified as the major CYP isozyme responsible for the metabolism of LDK378. An inhibition DDI study conducted in healthy volunteers indicated that ketoconazole (200 mg bid for 14 days), a strong CYP3A inhibitor, increased the Cmax and AUCinf of a single 450 mg oral dose of LDK378 by 1.2-fold and 2.9-fold, respectively, compared with LDK378 alone [REDACTED]. Therefore, concurrent use of strong CYP3A inhibitors should be avoided. An induction DDI study conducted in healthy volunteers indicated that rifampin (600 mg daily for 14 days), a strong CYP3A inducer, decreased the Cmax and AUCinf of a single 750 mg oral dose of LDK378 by 44% and 70%, respectively, compared with LDK378 alone [REDACTED]. Concurrent use of strong CYP3A inducers should be avoided.

A food effect study was conducted in healthy volunteers [REDACTED]. Compared to the fasted state, a low-fat meal increased Cmax and AUCinf of a single oral dose of LDK378 500 mg in healthy subjects by 43% and 58%, respectively, whereas a high-fat meal increased Cmax and AUCinf by 41% and 73%, respectively.

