After the fasted dose escalation has reached the MTD and/or RDE, the fed dose escalation will begin. The starting dose for the fed dose escalation part will be approximately 63% of the fasted MTD determined in this study. This is based on the data from adult healthy volunteers taking LDK378 with a low-fat meal. It is estimated that the steady state exposure of LDK378 with a low-fat meal will be increased 1.58 fold. Dose escalations during the fed dose escalation part of the study will be limited to a 25% or smaller increase above the prior fed dose level. It is anticipated that approximately 12-24 patients will be treated during the fed dose escalation. The same 2-parameter form of the BLRM will be used to estimate the dose-DLT relationships separately for fed patients. Data from fasted patients will be utilized to formulate a prior distribution for the BLRM parameters for fed patients. Details of the statistical model can be found in Section 14.1.3 of protocol.

Both fasted and fed dose escalation will continue until identification of the corresponding MTD or a suitable lower dose for expansion. This will occur when the following conditions are met:

1. at least 6 patients have been treated at this planned dose (initially assigned dose level (mg/m²) on Cycle 1 Day 1).
2. the dose satisfies one of the following conditions:
 - a. the posterior probability of targeted toxicity at this dose exceeds 50% and is the highest among potential doses, or
 - b. minimum number of patients (15 for the fasted state dose escalation, 12 for the fed state dose escalation) have already been treated on the trial.
3. it is the dose recommended for patients, either per the model or by review of all clinical data by Novartis and Investigators in a dose-escalation teleconference.

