2.2 Analysis sets

A patient is considered to be enrolled into the study if they have signed study informed consent. Only patients who have signed study informed consent prior to study procedures will be included in the analysis data sets.

Full analysis set

The Full Analysis Set (FAS) includes all patients who received at least one dose of LDK378. Patients will be classified according to the intended/planned treatment. The FAS will be used for all listings of raw data. Unless otherwise specified, the FAS will be the default analysis set used for all analyses.

The planned treatment will be based on the first dosing record. The corresponding fasted/fed status will be determined as per [Table 2-1](#) below as per protocol.

Table 2-1 Dose level and fasted/fed status

Dose Levels	Fasted/Fed Status
200 mg/m ²	Fasted
300 mg/m ²	Fasted
450 mg/m ²	Fasted
510 mg/m ²	Fasted
560 mg/m ²	Fasted
320 mg/m ²	Fed
400 mg/m ²	Fed
500 mg/m ²	Fed

Safety set

The safety set includes all patients who received at least one dose of LDK378.

The patients will be classified according to treatment received, where treatment received is defined as:

1. The actual dose level (mg/m^2) is the planned dose level if any actual total daily dose administered is equal to the value of “the planned dose levels ([Table 2-1](#)) * BSA (m^2) rounds to the nearest 50 mg”. For 25/75 mg, either rounding up or rounding down is acceptable.
2. The first actual dose level in the study (converts actual total daily dose administered / BSA (m^2) and maps to nearest planned dose levels) if the planned dose level was never received.

BSA = The last available BSA measurement on or before dosing date will be used in the calculation for actual dose level.

For example, if a patient from 500 mg/m^2 fed group doesn't meet the first criteria, and the first actual dose level in the study is 150 mg. Suppose this patient has BSA=0.45 m^2 on/before the first dose, then the first actual dose level in the study=actual total daily dose administered / BSA (m^2)=333 mg/m^2 , which will be rounded to the nearest planned dose level 320 mg/m^2 fed.

Dose determining set

The dose determining analysis set (DDS) consists of all patients from the safety set who *either* meet the minimum exposure criterion and have sufficient safety evaluations *or* discontinue earlier due to DLT in the escalation phase.

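### The dose-proportionality slope pools fasted and fed patients without a regimen term, and the trough-variability code omits the treatment effect that SAP 2.10 specifies

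*SAP*

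**What the plan says.** **Dose proportionality.** SAP 2.10 models ln(PK) = α + β·ln(dose), with dose as actual mg/m², on Cycle 1 Day 1 and on Cycle 2 Day 1. The data instruction is: "Data from both dose-escalation phase and expansion phase will be used. AUC0-24h and Cmax will be analyzed. All dose levels will be included". It reports β with a 90% CI and compares it informally with a target range, adding that "the actual result rather than the comparison itself should be emphasized when interpreting data". Neither a regimen covariate nor a fit per regimen is mentioned. Protocol 10.7.2.2 asks only for graphs and a model-based method.

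**Dose and regimen.** SAP 2.2 ("Table 2-1 Dose level and fasted/fed status") lists 200, 300, 450, 510 and 560 mg/m² as fasted and 320, 400 and 500 mg/m² as fed. No level is shared.

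**Food effect.** SAP 1.1 states: "It is estimated that the steady state exposure of LDK378 with a low-fat meal will be increased 1.58 fold". Protocol 1.2.1.2.4 gives the adult source: a low-fat meal raised Cmax and AUC "of a single oral dose of LDK378 500 mg in healthy subjects by 43% and 58%, respectively".

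**Sampling.** SAP 2.10: "During the expansion phase, blood samples for full plasma concentration-time profile of ceritinib are collected over 24 hours on Cycle 2 Day 1". The expansion part has no full profile on Cycle 1 Day 1.

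**Trough variability.** For patients at the MTD, SAP 2.10 names treatment as a fixed effect and patient as a random effect, and refers to 5.7 for detail. The PROC MIXED code in 5.7 has only patient in CLASS, nothing on the right-hand side of MODEL, and no BY statement. SAP 2.5 gives the MTD/RDE as 510 mg/m² fasted and 500 mg/m² fed, so two regimens enter. Table 4-1 mentions neither point.

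**The concern.** When regimen is tied to dose level and also changes exposure, leaving it out loads part of the food effect onto the dose slope. β then does not estimate proportionality in either regimen, although β is the result the SAP tells readers to emphasize. The rest of the plan keeps the regimens apart: the concentration and parameter summaries in SAP 2.10 and the toxicity model in SAP 2.5.2 are all separate for fasted and fed.

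The two fits also use different regimen mixes, because expansion patients contribute only to Cycle 2 Day 1. The bias can differ in sign between days and look like a change in proportionality from single dose to steady state. Protocol 1.2.1.2.4 already reports dose-proportional single-dose exposure and more-than-proportional steady-state troughs in adults, so such an artefact could pass as real.

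For troughs, a programmer following 5.7 would put any regimen difference into the patient variance and report a different inter-patient CV from the one 2.10 defines.

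**Working it through.** The plan gives no numerical result for either analysis, so there is no figure to reproduce. One input can be checked: 1/1.58 = 0.63, which matches the fed starting dose of about 63% of the fasted MTD.

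**Inputs**
- Escalation, Protocol Amendment 6: "40 patients have been enrolled and treated (25 fasted and 15 fed"). These form the Cycle 1 Day 1 data.
- Expansion: 7 fasted (Amendment 6). With 83 treated in total (Amendment 8), fed expansion = 83 - 40 - 7 = 36. Cycle 2 Day 1 therefore has 25 + 7 = 32 fasted and 15 + 36 = 51 fed.
- Assumed, because counts per level are not documented: at least 3 patients at 300, 450 and 560 fasted and at 320 and 400 fed; at least 6 at 510 fasted and 500 fed; 200 mg/m² unused; expansion patients at the RDE; every patient evaluable. This gives 2860 possible splits.
- Fed/fasted exposure ratio R: 1.58 (AUC) and 1.43 (Cmax) from adults, and 1.25 as an assumed smaller effect.

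**Bias in β** = ln(R) × cov(fed, ln dose) / var(ln dose), where cov = p(1-p) × (mean ln dose fed - mean ln dose fasted) and p is the fed share.

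*Worked split*: fasted 6/6/8/5 at 300/450/510/560, fed 4/4/7 at 320/400/500, R = 1.58, ln R = 0.457.
- Cycle 1 Day 1: p = 15/40; mean ln dose 6.036 fed, 6.096 fasted; cov = 0.234 × (-0.0596) = -0.0140; var = 0.0474. Bias = 0.457 × (-0.295) = -0.13, so a true β of 1 is estimated as 0.87.
- Cycle 2 Day 1: p = 51/83; mean ln dose 6.162 fed, 6.126 fasted; cov = 0.237 × 0.0360 = 0.0085; var = 0.0281. Bias = 0.457 × 0.304 = +0.14, so β is 1.14.
- With a regimen term, β is 1.00 on both days.

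*All 2860 splits:*

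| R | Cycle 1 Day 1 range (median) | Cycle 2 Day 1 range (median) |
|---|---|---|
| 1.58 | -0.46 to +0.22 (-0.20) | -0.25 to +0.42 (+0.08) |
| 1.43 | -0.36 to +0.18 (-0.15) | -0.20 to +0.33 (+0.06) |
| 1.25 | -0.22 to +0.11 (-0.10) | -0.12 to +0.21 (+0.04) |

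**Scale.** Over planned doses 300-560, the half-width of the SAP's target range is ln(1.25)/ln(560/300) = 0.36 (the SAP uses actual doses, so this is approximate). At R = 1.58 the bias exceeds it in 13% of Cycle 1 Day 1 splits and 1% of Cycle 2 Day 1 splits; at 1.43 and 1.25, in none. If at least 3 patients received 200 mg/m², the half-width is ln(1.25)/ln(560/200) = 0.22, and the bias at 1.58 is -0.10 to +0.21 on Cycle 1 Day 1 and +0.07 to +0.37 (median +0.24) on Cycle 2 Day 1.

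**Precision.** Protocol 1.2.1.2.4 gives single-dose AUC and Cmax variability: "The corresponding values in patients were 93% and 87% following single oral doses of 50 to 750 mg". With CV between 60% (assumed) and 93%, the 90% CI half-width of β with a regimen term is about 0.7-1.0 on Cycle 1 Day 1 and 0.6-0.9 on Cycle 2 Day 1. The median biases are a fraction of one standard error.

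**Trough CV.** Reported CV = sqrt(exp(ln(1+CV²) + p(1-p)·ln(R)²) - 1), with p here the fasted share at the RDEs. The splits imply 6-16 + 7 = 13-23 fasted and 6-9 + 36 = 42-45 fed patients. At R = 1.58, ln(R)² = 0.209 and the added variance is 0.036-0.048: 40% becomes 45-47%, 60% becomes 64-65%, and 93% becomes 97-98%. At 1.25 the excess is about 1-2 points. A mixed-model simulation (64 patients, 75% fed, true CV 42%, R = 1.58) gave 47.6% with the 5.7 code and 42.2% with treatment added. Intra-patient CV was 30.6% either way.

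**The case against.** - **The 1.58 ratio is probably high.** It compares an adult low-fat meal with fasting. Here the fed snack has 1.5-2 g of fat, and under Protocol 6.1.2 fasted patients also take each dose with 1-2 tablespoons of food. This stands: 1.58 is a high-end scenario, and the true contrast is undocumented.
- **Some splits are unlikely.** Planned size is 3-6 per level, although repeat cohorts are allowed. Capping fasted non-RDE levels at 6 leaves 640 splits. At 1.58, Cycle 2 Day 1 bias narrows to -0.18 to +0.23 (median +0.03, none beyond 0.36). Cycle 1 Day 1 does not improve: -0.45 to -0.02, median -0.24, with 16% beyond 0.36.
- **Evaluable counts are unknown.** SAP 2.2 excludes profiles for vomiting, off-plan dosing or prandial deviations. This stands, so the ranges are illustrative.
- **The practical weight is low.** The comparison is informal and unpowered, β is imprecise, and graphs and separate summaries would show a regimen difference. This limits priority, but those displays do not correct β.
- **The SAP reports β for each case, which might mean each regimen.** It never says so. The cases it names are two parameters and two days, under an instruction to include all levels.
- **The trough point is a text/code mismatch.** That is so. Section 2.10 has the right model, and the two sections must still be made to agree.

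**Conclusion.** Both points hold as written. On its plain reading, the dose-proportionality model confounds dose with regimen, and the 5.7 code does not fit the model that 2.10 specifies. No other section repairs either.

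The facts of the text are certain; the size and direction of the bias are not. They depend on undocumented counts per level and on an undocumented paediatric food effect, and the bias could be near zero if mean doses happen to balance. For trough no food effect is documented at all, so that inflation is illustrative. The MTD/RDE came from the toxicity model, so no dose or response-rate conclusion depends on either output. This is a secondary pharmacokinetic correction that should be made.

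**What to change.** In SAP 2.10, fit ln(PK) = α_regimen + β·ln(actual dose), with regimen as a factor, and examine the regimen by ln(dose) interaction; or state that fasted and fed are fitted separately. Under a common slope this removes the bias from this source.

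In SAP 5.7, use `CLASS patient treatment; MODEL Log_Ctrough = treatment / solution; RANDOM patient;` and amend the accompanying sentence so that it matches 2.10.

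The cost is one line of text, one line of code and one degree of freedom, with no new data. At R = 1.58 and CV 60-93%, the interval for β becomes slightly wider in 8-29% of Cycle 1 Day 1 splits and 0-4% of Cycle 2 Day 1 splits, and narrower in the rest.
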